10. MEASUREMENTS

10.1 Primary and Secondary Outcome measures

Primary Outcome

- Outcome 1 (Primary) Title: Clinical Response
- Outcome Description: Clinical response was assessed per the Response Evaluation Criteria in Solid Tumors (RECIST) v1.1 criteria.
 - Complete response (CR) = Disappearance of all target lesions; all lymph nodes < 10 mm on the short axis; no new lesions.
 - Partial response (PR) = $\geq 30\%$ decrease in the sum of the longest diameter of target lesions; no new lesions.
 - Stable disease (SD) = Small changes that do not meet any of the above criteria; no new lesions.
 - Progressive disease (PD) = 20% increase in the sum of the longest diameter of target lesions, and/or the appearance of one or more new lesion(s).

The outcome is expressed as the total number of participants who achieve a RECIST clinical response, defined as CR + PR, by 16 weeks, a number without dispersion. The outcome is expressed as the total number of participants who achieve a clinical response by 16 weeks, a number without dispersion.

- Outcome Timeframe: 16 weeks

Note: Per guidance from ClinicalTrials.gov, a single Primary Outcome is declared. Other primary and secondary objectives are reflected as secondary outcomes.

Secondary Outcomes

- Outcome 2 (Secondary) Title: Partial Response (PR) Rate
 - Outcome Description: Clinical response was assessed per the Response Evaluation Criteria in Solid Tumors (RECIST) v1.1 criteria.
 - Complete response (CR) = Disappearance of all target lesions; no new lesions.
 - Partial response (PR) = $\geq 30\%$ decrease in the sum of the longest diameter of target lesions; no new lesions.
 - Stable disease (SD) = Small changes that do not meet any of the above criteria; no new lesions.
 - Progressive disease (PD) = 20% increase in the sum of the longest diameter of target lesions, and/or the appearance of one or more new lesion(s)

The outcome is expressed as the total number of participants who achieve PR by 16 weeks, a number without dispersion.

- Outcome Timeframe: 16 weeks
- Outcome 3 (Secondary) Title: Stable Disease (SD) Rate
 - Outcome Description: Clinical response was assessed per the Response Evaluation Criteria in Solid Tumors (RECIST) v1.1 criteria.
 - Complete response (CR) = Disappearance of all target lesions; no new lesions.
 - Partial response (PR) = $\geq 30\%$ decrease in the sum of the longest diameter of target lesions; no new lesions.
 - Stable disease (SD) = Small changes that do not meet any of the above criteria; no new lesions.
 - Progressive disease (PD) = 20% increase in the sum of the longest diameter of target lesions, and/or the appearance of one or more new lesion(s)

The outcome is expressed as the total number of participants with SD at 16 weeks, a number without dispersion.

- Outcome Timeframe: 16 weeks
- Outcome 4 (Secondary) Title: Related Adverse Events (Toxicity)
 - Outcome Description: Adverse events were assessed per CTCAE version 5. The outcome is expressed as the total number of possibly, probably, or definitely-related adverse events experienced by participants, a number without dispersion.
 - Outcome Timeframe: 24 months

- Outcome 5 (Secondary) Title: Immune-related Clinical Response (irRECIST)
 - Outcome Description: The Immune-related Response Evaluation Criteria in Solid Tumors (irRECIST) vary from the RECIST criteria in order to distinguish cellular anti-tumor responses from tumor progression. This is primarily accomplished by specifying the minimum size to be considered a new tumor lesion. Clinical response was assessed per the irRECIST criteria.
 - Complete response (CR) = Disappearance of all target lesions; no new lesions $> 5 \times 5$ mm in size.
 - Partial response (PR) = $\geq 30\%$ decrease in the sum of the longest diameter of target lesions; no new lesions $> 5 \times 5$ mm in size.
 - Stable disease (SD) = Small changes that do not meet any of the above criteria; no new lesions $> 5 \times 5$ mm in size.
 - Progressive disease (PD) = 20% increase in the sum of the longest diameter of target lesions, and/or the appearance of one or more new lesion(s).

The outcome is expressed as the total number of participants who achieve an irRECIST clinical response, defined as CR + PR, by 16 weeks, a number without dispersion.

- Outcome Timeframe: 16 weeks
- Outcome 6 (Secondary) Title: Progression-free survival (PFS)
 - Outcome Description: 6-month Progression-free survival (PFS) as measured from the time of consent until death or disease progression. The outcome is expressed as the total number of participants remaining alive without disease progression at 6 months after consent, a number without dispersion.
 - Outcome Timeframe: 6 months

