3.4 Registration Process

No subject may begin study treatment prior to registration and assignment of a subject identification number.

At registration, Stanford will sequentially assign eligible subjects an identification number. The maximum allowable time between registration and the first administration of study treatment is 14 days. The subject's identification number will be used on all subject-specific Case Report Forms (CRFs) and serious adverse event (SAE) forms. Case report forms will be electronic. Participant information should be entered into OnCore within 5 business days.

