3.5 Study Timeline

Primary Completion: Primary completion is the date that the final datum is obtained / expected to be obtained for the primary outcome. The timeframe for primary completion for an individual subject is 16 weeks after initiation of treatment. This datum is expected to be obtained approximately 40 months from the time the study opens to accrual.

Study Completion: The study is expected to reach overall completion (last datum from last subject) approximately 60 months (5 years) from the time the study opens to accrual.

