- d. Tumor measurements are based on RECIST v1.1 and irRECIST criteria (Appendices C & D). Scans will be done at baseline within 28 days of 1st treatment and then after dose 4 of immunotherapy (W 10 dose). This scan should be done at week 14 ± 1 week and every 12 weeks ± 1 week, once subjects start maintenance nivolumab. Ablated tumors will not be included as part of the treatment response assessment, ie, disease response; measurable disease; or tumor progression, by either RECIST or irRECIST. The baseline measurements will be done before treatment, and follow-up measurements will be done after 4 doses of ipilimumab and nivolumab (12 weeks), then every 12 weeks thereafter. At Investigator's discretion, imaging of known sites of disease is recommended.
- e. Serum β-HCG: Women of child-bearing potential are required to have a negative pregnancy test within 24 hours (eligibility criteria) prior to the initial administration of study drug, then every 3 to 4 weeks (± 1 week) during the study (this test can be omitted if subject is post-menopausal by either surgery or elevated FSH).
- f. ACTH, serum cortisol, TSH, free T4, CRP, ESR.
- g. Archival tumor sample must be available at baseline. All subsequent biopsies will be collected in paraffin for research purposes and standard diagnostics. Blood will be collected at baseline, and prior to treatment dose on weeks 1, 4, 7, 10 and during the off-study visit. Off study visit with a ± 1 week.
- h. Per protocol cryoablation is required to be performed before Week 4 administration of ipilimumab and nivolumab. (between Cycle 1 and Cycle 2), at the discretion of the investigator.
- i. Safety follow-up: After the off-study visit, there will be two additional follow-up phone call/or retrieval of medical records that occur every 35 days ± 1 week to collect information on participants' health status.

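### Six-month PFS is counted from consent but on-study scans are timed from first dose, so a long consent-to-dose delay can put the second scan after the landmark and overstate the rate

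*Combined protocol and SAP*

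**What the plan says.** Outcome 6 in Section 10.1 takes consent as the origin ("6-month Progression-free survival (PFS) as measured from the time of consent until death or disease progression") and reports a count at a fixed date: "The outcome is expressed as the total number of participants remaining alive without disease progression at 6 months after consent". Section 12 adds a Kaplan-Meier display of PFS. Section 1.2 lists the six-month rate as a secondary objective.

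The scans run on a different clock. The Study Calendar (Section 9) labels the first dose as week 1, and its footnote d makes two statements about follow-up imaging: "This scan should be done at week 14 ± 1 week and every 12 weeks ± 1 week, once subjects start maintenance nivolumab", and "follow-up measurements will be done after 4 doses of ipilimumab and nivolumab (12 weeks), then every 12 weeks thereafter". For baseline it says "Scans will be done at baseline within 28 days of 1st treatment". Section 4 has a third version: imaging at screening and then at 12-week intervals, plus or minus 7 days, with earlier scans when clinically indicated.

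On the delay between consent and treatment, Section 3.4 says "The maximum allowable time between registration and the first administration of study treatment is 14 days". Nothing limits the time from consent to registration. The primary endpoint uses treatment start as its origin (Section 3.5): "The timeframe for primary completion for an individual subject is 16 weeks after initiation of treatment".

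No section gives an assessment window around six months, or says how to count a patient whose second scan falls after it.

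**The concern.** A progression can only be counted once it has been found. If the landmark is fixed by the consent date and the second scan by the first-dose date, each day between consent and first dose brings the landmark a day closer to that scan, and a long enough delay puts the landmark first. A patient who progressed silently between the first and second scans is then recorded as progression-free at six months, both in the count and on the Kaplan-Meier curve. The error goes one way, upward, and its size varies with each patient's screening delay, which has nothing to do with treatment. That makes the rate hard to interpret or to compare with other studies.

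Delays of this length are allowed. Consent precedes any study-specific procedure (Section 3.3), the eligibility checklist must be complete before registration (Appendix A), and up to 14 more days may then pass before first dose.

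**Working it through.** The plan gives no expected rate, precision or sample size for six-month PFS, so there is no figure of its own to reproduce.

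**Thresholds.** Six months = 365.25/2 = 182.6 days = 26.09 weeks.
- 12 weeks, then 12 more: second scan at day 168. Threshold lag = 182.6 − 168 = 14.6 days.
- Calendar week 14 (13 elapsed weeks, because first dose is week 1), then 12 more weeks: day 175. Threshold lag = 182.6 − 175 = 7.6 days.
- A second scan one week late lowers these to 7.6 and 0.6 days. One week early raises them to 21.6 and 14.6 days.

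**Size of the excess.** Assumptions, none of them from the documents:
- PFS is exponential from first dose, with median m of 3 or 4 months. The roughly 60% three-month PFS that Section 12 cites for other drugs implies 3 × ln 2 / (−ln 0.6) = 4.07 months.
- Scans are uniform within ±1 week of dates fixed to first dose. The 12-week statement has no window of its own, so Section 4's 7 days is used.
- Progression is seen only at scheduled scans.

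Weekly hazard h = ln 2 / (m × 26.09/6), which is 0.0531 (m = 3) or 0.0399 (m = 4). S(t) = exp(−ht).

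At a 14-day lag the landmark is 26.09 − 2 = 24.09 weeks after first dose. The true rate is S(24.09) = 0.278 (m = 3) or 0.383 (m = 4).
- 25-week scan, window 24 to 26: share late = (26 − 24.09)/2 = 0.955. For m = 3, observed = 0.955 × S(13) + 0.045 × S(24.05) = 0.955 × 0.501 + 0.045 × 0.279 = 0.491. Excess +21 points. For m = 4, 0.586 against 0.383: +20 points.
- 24-week scan, window 23 to 25: share late = (25 − 24.09)/2 = 0.455. For m = 3, observed = 0.455 × S(12) + 0.545 × S(23.55) = 0.455 × 0.529 + 0.545 × 0.286 = 0.397. Excess +12 points. For m = 4, 0.495 against 0.383: +11 points.

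Simulation with 2,000,000 draws per cell agrees and gives the other rows:

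| Lag | 25-week scan: share late, excess | 24-week scan: share late, excess |
|---|---|---|
| 0 days | 0, +1.5 | 0, +3 |
| 7 days | 0.455, +11 | 0, +1.6 |
| 14 days | 0.955, +20 to 21 | 0.455, +11 to 12 |
| spread evenly over 0 to 14 days | 0.46, +11 | 0.10, +4 |

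For the 28 patients of the two-stage design, the 14-day row is at most about 28 × 0.21 = 6 or 28 × 0.115 = 3 patients. If half of the events were found as they occur (also an assumption), it falls to +10 to 11 or +6 points.

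**Section 4 read literally.** With a screening scan 0 to 7 days after consent, the second scan's window closes at most 25 + 1 = 26 weeks after consent, before 26.09, so none is late. For m = 3, dosing on day 14 gives a true rate of 0.278 against 0.311 (scan on day 0) or 0.295 (scan on day 7). Dosing on day 28 gives 0.309 against 0.346 or 0.328. The excess is about +2 to +4 points.

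**The schedules conflict.** With the baseline scan 14 days before first dose, Section 4 puts the first follow-up scan 9 to 11 weeks after first dose. The week-14 statement puts it at 12 to 14 weeks.

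**Counting from first dose.** The landmark is then 26.09 weeks after first dose for everyone.
- 24-week scan: S(24) = 0.279 against 0.250 (m = 3), +3 points.
- 25-week scan, windows fixed to first dose: S(25) = 0.265 against 0.250, +1.5 points.
- 25-week scan, each window running from the previous scan: share late = (2 − 1.09)²/8 = 0.10. Simulated 0.289 against 0.250 (m = 3) and 0.394 against 0.354 (m = 4), +4 points.

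**The case against.** The strongest reply is that the size depends on a lag the documents never give and on footnote d, not Section 4, governing the scans. That stands. A reader might infer that the reported rate will be about 20 points too high. The documents do not support that: the figure needs the 25-week reading, a 14-day lag, and no progression found between scheduled scans. Section 4 allows earlier scans when clinically indicated, and the calendar has a physical examination and performance status at every treatment visit. The 20-point figure is a ceiling.

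The 1.5 to 3 points at zero lag are ordinary interval-scanning error and cannot be blamed on the consent origin.

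It is also fair to say that the endpoint is descriptive. It has no hypothesis or threshold, and the two-stage rule uses response at 16 weeks. A reader might fear for the go/no-go decision, but nothing here touches it.

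Finally, one might want to remove from the progression-free count everyone who lacks a scan in a window before six months. That would overcorrect: a patient scanned shortly afterwards and found clear is known to have been progression-free at the landmark.

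What remains is that the two clocks differ, the lag is uncapped, and the plan has no rule for a scan that falls after the landmark.

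**Conclusion.** The concern holds in conditional form. If footnote d governs, the six-month rate as defined can be overstated by an amount that depends on screening delay, starting at a nominal lag of about 8 days (25-week scan) or 15 days (24-week scan), give or take a week. At a 14-day lag the upper bound is +20 to 21 or +11 to 12 points, under exponential PFS with a 3- to 4-month median and detection only at scheduled scans. If Section 4 is followed literally with a screening scan within 7 days after consent, the excess is a few points. The actual bias cannot be fixed from the documents. The point should be corrected because it affects a stated secondary objective and costs little to repair. Confidence in the size is only moderate.

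**What to change.** 1. Measure PFS from first dose, the origin Section 3.5 already uses for the primary endpoint. On the footnote d schedules this removes the dependence on the consent lag and cuts the upper-bound excess to about +3 points (24-week scan), or for the 25-week scan +1.5 points if the windows are fixed to first dose and about +4 if they run from the previous scan.
2. Reconcile Section 4 and the two statements in footnote d into one scan schedule with one stated anchor, and say whether the one-week windows are fixed to that anchor. The new origin is not enough alone. If a screening anchor were kept, a baseline scan 14 or 28 days before first dose would put the second scan at 22 or 20 weeks and leave about +6 or +10 points (m = 3: 0.311 or 0.346 against 0.250). If week 14 were meant as 14 elapsed weeks, about +10.5 points would remain at a 26.09-week landmark.
3. Report how many patients have no scan near the six-month landmark. Count a patient as progression-free if a later scan is clear. In the Kaplan-Meier analysis, censor patients with no later assessment at their last adequate scan.

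The cost is a change of wording and no added scans, although settling on one schedule may shift some scan dates slightly. The reported rate will usually be lower.

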1.2. Secondary Objectives

- a. Characterize the 6-month progression-free survival (PFS) rate**
- b. Assess whether the treatment yields a reasonably safe and tolerable profile**

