4.2 Criteria for Removal from Study

Subjects will be removed from study if they have disease progression; unacceptable adverse events in the opinion of the subject or the investigator; withdrawal of consent; non-compliance; or if subject is female and has become pregnant.

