12. STATISTICAL CONSIDERATIONS

We anticipate enrolling no more than 30 subjects to achieve our aims and this is feasible. Specifically, it is anticipated that 3 to 4 subjects per month may be enrolled onto this trial. Thus, it is expected that 12 months will be required to accrue the number of subjects necessary to complete the trial.

More specifically, clinical benefit (CR/PR/SD) will be assessed for each subject at 16 weeks. Our null hypothesis is that the response rate is $\leq 30\%$, and our alternative

hypothesis is that the response rate is $\geq 60\%$. The selection of 60% as a threshold for determining the treatment is worthy of further study is due to recent trials of sarcoma FDA-approved drugs showing ~60% PFS rate at 3 months (ie, pazopanib, trabectedin, eribulin).

We will employ a Simon 2-stage design to address our primary objective. The type 1 error rate assumed for the Simon 2-stage design is 0.04. The null hypothesis that the true response rate (ie, sum of CR and PR) is 30% or less will be tested against a one-sided alternative. Our decision rule works as follows. In the first stage, we will accrue and assess 10 subjects. If 3 or fewer subjects (< 30% of 10 subjects) achieve a clinical response, the trial will be stopped for futility. If more than 3 subjects achieve a clinical response, we will enroll and treat an additional 18 subjects. If 12 or fewer of the 28 treated subjects (< 42.8%) demonstrate a clinical response (either CR or PR), we will conclude the treatment is not worthy of further study. If, however, more than 12 of the 28 treated subjects ($\geq 42.8\%$) responds, we will claim the treatment promising.

Assuming a true response rate of 60%, we have 90% power to correctly conclude the treatment promising. In contrast, if the true response rate is only 30%, we have a low probability (0.04) of incorrectly continuing to study the treatment.

Additionally, we will characterize rates of toxicity by level of toxicity as well as by other subject-level characteristics.

To address secondary objectives, we will use Kaplan-Meier methods to graphically depict progression-free survival. This tool will also be used to demonstrate survival across various sub-groups of interest. Generalized linear regression methods (with a logit link) will be utilized to characterize relationships between features such as mutation burden, PDL1 expression, and tumor infiltrating lymphocytes and response.

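### The 6-month PFS rate is to be reported as a bare count, with no denominator, no rule for subjects of unknown status and no interval, and no Kaplan-Meier estimate at 6 months is specified

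*Combined protocol and SAP*

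**What the plan says.** The first secondary objective in Section 1.2 reads "Characterize the 6-month progression-free survival (PFS) rate". Its only operational definition is Outcome 6 in Section 10.1. Time to event is taken "as measured from the time of consent until death or disease progression", and the reported quantity is a count: "The outcome is expressed as the total number of participants remaining alive without disease progression at 6 months after consent". The same sentence goes on to say that the number carries no dispersion. No denominator, analysis set or censoring rule is given there, and nothing is said about a subject whose status at 6 months is not known.

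Section 12 says: "To address secondary objectives, we will use Kaplan-Meier methods to graphically depict progression-free survival". The sentence after it extends the method to sub-groups, and the synopsis says much the same. Neither place names an estimate at 6 months or a confidence interval, or says how the curve relates to the count.

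Subjects can leave without a PFS event. Besides progression and pregnancy, Section 4.2 lists "unacceptable adverse events in the opinion of the subject or the investigator; withdrawal of consent; non-compliance" as grounds for removal. The calendar in Section 9 marks no tumor measurement or imaging at the off-study visit or in follow-up. Its note i says that afterwards "there will be two additional follow-up phone call/or retrieval of medical records that occur every 35 days", to learn about health status. No dropout rate is stated anywhere.

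**The concern.** The objective is a rate and the outcome is a count. To get from one to the other, someone must choose a denominator and decide what to do with subjects who left before 6 months without progressing or dying. The plan makes neither choice, so both could be made after the data are seen, and different choices give different rates from the same data. The count may also disagree with the Kaplan-Meier curve shown beside it, with nothing to say which governs. With at most 30 subjects the sampling uncertainty is large, and Outcome 6 as written reports none of it.

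**Working it through.** **1. The plan's own figures.** There are none for PFS: no target rate, power or precision. The only design figures belong to the Simon rule for response (stop at 3 or fewer of 10; promising if more than 12 of 28). They reproduce: power 0.912 at 60% against 90% stated, and type I error 0.0419 at 30% against 0.04 stated. They do not involve PFS.

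**2. Can status at 6 months be unknown?** Take the off-study visit as 30 days after the last dose, with two contacts 35 days apart after it. Scheduled contact then ends 30 + 2 × 35 = 100 days after the last dose. For a subject whose last dose is at Week 7 (day 43) that is day 143. Adding the 14 days that Section 3.4 allows between registration and first dose gives day 157. Six months is about day 183. These contacts include no imaging. So the protocol does not secure 6-month progression status for subjects who stop early.

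**3. What loss does to the rate.** These inputs are assumptions, not figures from the documents: true 6-month PFS S of 20% to 50%; probability d of 5% to 20% that a subject's censoring time falls before 6 months; exponential event and censoring times, independent of each other. With λ = −ln S and c = −ln(1 − d):

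- known event-free at 6 months: A = S × (1 − d)
- event observed before 6 months: E = λ/(λ + c) × (1 − A)
- observed as censored before 6 months: C = 1 − A − E

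For S = 40%, d = 10%: A = 0.40 × 0.90 = 0.360; E = 0.916/1.022 × 0.640 = 0.574; C = 0.066. In 28 subjects the expected count is 10.1, against 11.2 truly event-free.

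| S | d | Censored, C | Left out, over all N: A | Dropped from denominator: A/(A + E) | Counted as progression-free: A + C |
|---|---|---|---|---|---|
| 20% | 5% | 2.5% | 19.0% | 19.5% | 21.5% |
| 20% | 20% | 10.2% | 16.0% | 17.8% | 26.2% |
| 40% | 5% | 3.3% | 38.0% | 39.3% | 41.3% |
| 40% | 10% | 6.6% | 36.0% | 38.5% | 42.6% |
| 40% | 20% | 13.3% | 32.0% | 36.9% | 45.3% |
| 50% | 5% | 3.6% | 47.5% | 49.3% | 51.1% |
| 50% | 20% | 14.6% | 40.0% | 46.8% | 54.6% |

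The average bias is −1.0 to −10.0 points (equal to −S × d) if unknowns are left out over all N, −0.5 to −3.2 points if they are dropped from the denominator, and +1.1 to +6.2 points if they are counted as progression-free. Note that d is larger than the share actually seen as censored: at S = 40%, d = 10% corresponds to about 2 of 28 subjects (0.066 × 28 = 1.8).

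**4. A single invented data set.** N = 28; censored at 1.5, 3.5 and 5 months; 8 events at 3.3 months and 6 at 5.9 months; 11 subjects event-free beyond 6 months.

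- Count over N: 11/28 = 39.3%
- Unknowns counted as progression-free: 14/28 = 50.0%
- Kaplan-Meier: (19/27) × (11/17) = 45.5%; Greenwood SE = 0.455 × √(8/(27 × 19) + 6/(17 × 11)) = 9.9 points

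With no censoring, the count over N and Kaplan-Meier agree.

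**5. Precision left out.** The exact 95% interval for 11/28 is 21.5% to 59.4%; for 12/30 it is 22.7% to 59.4%.

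**6. The landmark and the scan.** Note d in Section 9 puts the first scan at week 14 ± 1 and the next 12 weeks later, so about weeks 25 to 27 from first treatment. Six months is 26.1 weeks, counted from consent. With a consent-to-treatment lag of 1 week the second scan falls at weeks 26 to 28 from consent; with 2 weeks, at weeks 27 to 29. Status at 6 months may then rest on the first scan, at week 16 from consent under a 2-week lag. If progression were found only at scheduled scans and S = 40%, Kaplan-Meier at 6 months would read 0.40^(16/26.1) = 57.0%, and the count over N with d = 10% would read 0.90 × 57.0% = 51.3%. Unscheduled scans, or the plain 12-weekly schedule also given in Section 4 and in part of note d, would reduce this.

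**The case against.** The case for leaving the plan alone has four parts.

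- **Kaplan-Meier is already the named method.** Section 12 introduces it as the way to address the secondary objectives, and a curve can be read at 6 months. This stands. A reader might infer that Kaplan-Meier is there only as a picture and that the rate bypasses it; the text does not support that. What is missing is a commitment to the 6-month estimate and its interval.
- **Section 10.1 reads like registry text.** It cites registry guidance, and every outcome is worded as a number without spread. But that guidance is cited only for declaring a single primary outcome, and Outcome 6 is the only definition of this endpoint.
- **Counting unknowns as failures is a recognised conservative convention** for a landmark in a single-arm study, and an exact interval follows from a count and N. True, but the plan states neither the convention nor N.
- **The endpoint is descriptive,** with no hypothesis or threshold. This stands and limits the consequence.

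A reader might also infer that each subject censored before 6 months pulls the result down. The documents do not support that. A censored subject who would have progressed anyway does not change the count, the effect is an average, and its direction depends on handling that is not stated. Nor is everyone removed under Section 4.2 a wrongly counted failure: progression is a listed reason and is a genuine event.

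**Conclusion.** The gap is real: a secondary objective framed as a rate is defined as a count without denominator, missing-status rule or precision, and no Kaplan-Meier estimate at 6 months is specified. On the most literal reading (only known event-free subjects counted, over all N) the implied rate is too low on average by S × d, which is 1 to 10 points over the assumed range and 4 points at S = 40%, d = 10%. Counting unknowns as progression-free reverses the sign. These sizes rest on assumed PFS and dropout and on independent exponential times; the documents give no rate that would fix them.

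It would also be too strong to infer that Kaplan-Meier recovers the true rate. That needs non-informative censoring and well-observed event times. Removals for toxicity or non-compliance may be informative, and a scan near week 26 from treatment start may fall after a landmark counted from consent. The net direction of error is therefore not established. Kaplan-Meier with an interval is still the better summary, because it uses the time each lost subject was followed and shows its uncertainty. Only this descriptive secondary endpoint is affected.

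**What to change.** In Sections 10.1 and 12:

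- Define the 6-month PFS rate as the Kaplan-Meier estimate at 6 months in treated subjects, with a 95% confidence interval of a named type.
- Censor subjects without an event at the last adequate tumor assessment.
- State how the scan due near week 26 from treatment start is assigned to a landmark measured from consent, and reconcile the scan timings given in Section 4 and in note d of Section 9.
- Keep the count as a supplementary figure with its denominator and the number of unknown status. With unknowns taken as failures it serves as the conservative sensitivity figure if censoring is informative.

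The cost is a few sentences. The Kaplan-Meier fit is already planned, no new data are needed, and the Simon decision does not change.
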